6.5. Concomitant Therapy

Participants will be permitted to use concomitant medications that they require during the study, except certain medications that may interfere with the assessment of efficacy and safety characteristics of the study intervention(s) (see [Table 10](#)).

Investigative site staff will inform participants that they must consult with the investigator or a designated site staff member upon being prescribed any new medications during the study. This may not be possible when initiated for treatment of medical emergencies, in which case the participant will inform the investigator or a designated site staff member as soon as possible.

Any medication or vaccine, including over-the-counter or prescription medicines and vitamins, or other specific categories of interest, that the participant is receiving at the time of enrollment or receives during the study, must be recorded on the "Concomitant Medications" section of the eCRF, along with

- reason for use
- dates of administration, including start and end dates, and
- dosage information, including dose and frequency for concomitant therapy of special interest (that is, any other glucose lowering medication).

The medical monitor should be contacted if there are any questions regarding concomitant or prior therapy.

Antihyperglycemic medications other than study intervention(s) and metformin, if applicable, are not allowed at any time during the study except

- as allowed for those participants who require permanent discontinuation of study intervention (that is, tirzepatide or insulin lispro [U100]), but remain in the study
- as rescue therapy, 24 weeks after randomization due to severe, persistent hyperglycemia (see Section 8.3.6.2.), or
- during the safety follow-up period.

Glucagon-like peptide-1 receptor agonist, DPP-4is, pramlintide, other basal insulins (except insulin glargine [U100]), and other prandial insulins (except insulin lispro [U100]) are prohibited medications and are not allowed as rescue therapies. Short-term treatment with a nonstudy insulin for less than 14 days is allowed for certain clinical situations, such as elective surgery, during hospitalization, or hyperosmolar states.

After randomization, discontinuation of metformin or change in dosage and formulation is not permitted, except in the following situations:

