6.6.3. Management of Participants with Gastrointestinal Symptoms

The tirzepatide dose escalation scheme has been designed to minimize the development of GI symptoms. During the dose escalation period, every effort should be made by the investigator to escalate and maintain participants on the corresponding tirzepatide dosage.

Dose escalation period for different doses of tirzepatide is defined as

- Weeks 0 to 8 for maintenance dose of tirzepatide 5 mg
- Weeks 0 to 16 for maintenance dose of tirzepatide 10 mg
- Weeks 0 to 24 for maintenance dose of tirzepatide 15 mg

To mitigate GI symptoms and manage participants with intolerable GI AEs during the escalation period for respective maintenance doses of tirzepatide, the investigator should follow these steps (see [Table 11](#)):

Table 11. Mitigation of Gastrointestinal Symptoms

STEP 1	Advise participants to eat smaller meals, for example, splitting 3 daily meals into 4 or more smaller meals, and to stop eating when they feel full.
STEP 2	Continue STEP 1 + Prescribe symptomatic medication, for example, anti-emetic or anti-diarrheal medication, per local country availability and individual participant needs. Use of symptomatic medication should be captured as concomitant medication in the eCRF.
STEP 3	Continue STEP 1 + STEP 2 + Temporarily interrupt tirzepatide; omit 1 dose, the participant will take 3 of 4 doses at that dose level. After the interruption, restart at the same dose with the participant taking medication to alleviate their GI symptoms. The data related to temporary interruption of study treatment should be documented in source documents and entered on the eCRF.
STEP 4	If intolerable GI symptoms or events persist despite the above measures, the investigator may decide to discontinue tirzepatide permanently. Participants who stop tirzepatide permanently will intensify insulin treatment and/or receive another glucose-lowering intervention (Section 7.1) and will continue participating in the study according to the protocol to collect all planned efficacy and safety measurements. The new glucose-lowering intervention will be recorded on the eCRF specified for collecting anti-hyperglycemic medications.

Note: De-escalation of tirzepatide will not be allowed.

Abbreviations: eCRF = electronic case report form; GI = gastrointestinal.

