- Any other TEAE, SAE, or clinically significant laboratory value for which the investigator believes that permanent study intervention discontinuation is the appropriate measure to be taken
- If a participant misses 3 or more consecutive doses of tirzepatide due to intolerable GI symptoms (that is, nausea, vomiting, or diarrhea) that could be reasonably attributed to tirzepatide, despite following the mitigation steps per Section 6.6.3.
- If female participant becomes pregnant (see Section 8.3.5.)

Note: Participant will be discontinued from the study, as well.

- If a participant is diagnosed with T1DM

Note: Participant will be discontinued from the study, as well.

Participants who permanently stop tirzepatide or insulin lispro (U100) will continue to titrate insulin glargine (U100) and receive another glucose-lowering intervention, if needed per clinical judgment of investigator, and will continue participating in the trial according to the protocol to collect all planned efficacy and safety measurements.

Participants discontinuing tirzepatide or insulin lispro (U100) prematurely for any reason should complete AE and other follow-up procedures per this protocol.

See Section 1.3. for data to be collected at the time of intervention discontinuation and follow-up and for any further evaluations that need to be completed.

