7.2. Participant Discontinuation/Withdrawal from the Study

A participant may withdraw from the study

- at any time at his or her own request
- at the request of his or her designee, for example, parents or legal guardian
- at the discretion of the investigator for safety, behavioral, compliance, or administrative reasons
- if enrollment in any other clinical study involving an investigational product or enrollment in any other type of medical research judged not to be scientifically or medically compatible with this study, or
- if the participant, for any reason, requires treatment with another therapeutic agent that has been demonstrated to be effective for treatment of the study indication, discontinuation from the study occurs prior to introduction of the new agent.

A participant will be withdrawn from the study:

- if a female participant becomes pregnant
- if a participant is diagnosed with T1DM.

Discontinuation is expected to be uncommon.

At the time of discontinuing from the study, if possible, an early termination visit should be conducted, as shown in the SoA. See Section [1.3](#). for data to be collected at the time of study

discontinuation and follow-up and for any further evaluations that need to be completed. The participant will be permanently discontinued both from the study intervention and from the study at that time.

If the participant withdraws consent for disclosure of future information, the sponsor may retain and continue to use any data collected before such a withdrawal of consent. If a participant withdraws from the study, he or she may request destruction of any samples taken and not tested, and the investigator must document this in the site study records.

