8.3.6.2. Severe, Persistent Hyperglycemia

Severe, persistent hyperglycemia episodes will be collected during the trial to assess the risk of extreme imbalance in glycemic control.

Note: The criteria for evaluation of severe, persistent hyperglycemia will only be applicable after Week 24.

Investigators will be trained on the application of criteria for deciding when and how to intervene with participants experiencing severe persistent hyperglycemia. Evaluation should be made if participant is compliant to study intervention(s) and has appropriately titrated the dose of insulin glargine (U100) and/or insulin lispro (U100), if applicable, prior to asserting if severe, persistent hyperglycemia criteria has been met. Insulin glargine (U100) and/or insulin lispro (U100), if applicable should be titrated first before adding any rescue therapy. Protocol allowed rescue therapies may be added thereafter in participants who meet the severe, persistent hyperglycemia criteria at the discretion of investigator in accordance with American Diabetes Association/European Association for the Study of Diabetes guidance.²⁶ Rescue medication will be prescribed as add-on to study intervention(s), and participants will continue to follow the protocol-specified visit schedule.

Add-on glycemic rescue therapy will be allowed for participants who met any 1 of the following prespecified criteria for severe, persistent hyperglycemia and no intercurrent cause of the hyperglycemia identified. Investigators should first confirm that the participant is fully compliant with the assigned therapeutic regimen and that the participant does not have an acute condition causing severe hyperglycemia:

- average daily BG from the weekly 4-point SMBG (fasting BG, pre-second meal BG, pre-third meal BG, and bedtime BG) profile is >200 mg/dL (>11.1 mmol/L) over a consecutive 2-week period at any time beyond the first 24 weeks post-randomization, or
- HbA1c $\geq 8.5\%$ (69 mmol/mol) after 24 weeks, with inadequate response to the existing regimen defined as improvement in HbA1c over the last 3 months that is, $<0.3\%$

Rescue therapy option:

Rescue treatment with pramlintide, DPP-4is, GLP-1 RAs, other basal insulins (except insulin glargine [U100]), or other prandial insulins (except insulin lispro [U100]), will not be allowed (see Section 6.5.).

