8.3.6.3. Pancreatitis

Diagnosis of acute pancreatitis

Acute pancreatitis is defined as an AE of interest in all trials with tirzepatide including this trial. Acute pancreatitis is an acute inflammatory process of the pancreas that may also involve peripancreatic tissues and/or remote organ systems.²⁷ The diagnosis of acute pancreatitis requires 2 of the following 3 features:

- abdominal pain, characteristic of acute pancreatitis (generally located in the epigastrium and radiates to the back in approximately half the cases;^{27,28} the pain is often associated with nausea and vomiting)
- serum pancreatic amylase and/or lipase $\geq 3X$ ULN, and
- characteristic findings of acute pancreatitis on CT scan or magnetic resonance imaging.

If acute pancreatitis is suspected, the investigator should

- obtain appropriate laboratory tests, including levels of pancreatic amylase and lipase, via the central laboratory and, if needed, via a local laboratory as well, and
- perform imaging studies, such as abdominal CT scan with or without contrast, magnetic resonance imaging, or gallbladder ultrasound.

Discontinuation and rescue intervention for acute pancreatitis

If laboratory values and/or abdominal imaging support the diagnosis of acute pancreatitis, the participant must discontinue therapy with investigational product(s), but will continue in the study on another glucose-lowering regimen (details on rescue intervention will be provided). The most appropriate diabetes therapeutic regimen will be decided by the investigator, based on the participant's clinical status. A review of the participant's concomitant medications should be conducted to assess any potential causal relationship with pancreatitis.

Reporting adverse events and serious adverse events of acute pancreatitis

Each event of pancreatitis must be reported as an AE or SAE.

The investigator must report the event as an SAE if the typical signs and/or symptoms of pancreatitis

- are present, and
- are confirmed by

- laboratory values (lipase or amylase [total and/or pancreatic]), and
- imaging studies.

If a potential event does not meet all of these criteria, the investigator will decide the seriousness of the event, either AE or SAE.

The investigator will also review the participant's concomitant medications to assess any potential causal relationship with pancreatitis and will report the relatedness of study intervention(s) to the event.

Pancreatic hyperenzymemia

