8.3.6.7. Hypersensitivity Events

Many drugs, but particularly biologic agents, carry the risk of systemic hypersensitivity reactions. If such a reaction occurs, additional data describing each symptom should be provided to the sponsor in the eCRF.

The sites should have appropriately trained medical staff and appropriate medical equipment available when study participants are receiving study intervention(s). It is recommended that participants who experience a systemic hypersensitivity reaction be treated per the local standard of care.

In the case of generalized urticaria or anaphylaxis, additional blood samples should be collected as described in Section 10.3. Laboratory results are provided to the sponsor via the central laboratory. Investigational product should be temporarily interrupted in any individual suspected

of having a severe or serious allergic reaction to investigational product. Investigational product may be restarted when/ if it is safe to do so, in the opinion of the investigator. If investigational product is permanently discontinued, the participant will continue to adjust the dose of insulin glargine (U100) and may receive another glucose-lowering treatment, judged by the investigator to be appropriate based on the participant's clinical status, and will continue in the trial to collect all planned efficacy and safety measurements.

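### Protocol 7.2 provides for study exit before any other effective glucose-lowering agent is started, while six other sections keep the same participants in follow-up on such agents

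*Protocol*

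**What the plan says.** Protocol 7.2 has two lists. The first gives circumstances in which a participant may withdraw. Its last item applies when a participant, whatever the reason, needs another agent shown to be "effective for treatment of the study indication, discontinuation from the study occurs prior to introduction of the new agent". The second list, of those who will be withdrawn, names only pregnancy and type 1 diabetes. On leaving the study, 7.2 continues: "The participant will be permanently discontinued both from the study intervention and from the study at that time".

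Other sections give a different rule for participants who need another glucose-lowering agent:

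- **6.5** permits other antihyperglycemic drugs "as allowed for those participants who require permanent discontinuation of study intervention (that is, tirzepatide or insulin lispro [U100]), but remain in the study", and as rescue from 24 weeks after randomization. Table 10 lists the permitted and prohibited classes.
- **6.6.3, Step 4** (intolerable gastrointestinal symptoms): participants who stop tirzepatide intensify insulin, receive another agent, or both, and "will continue participating in the study according to the protocol to collect all planned efficacy and safety measurements".
- **7.1**: those who permanently stop tirzepatide or lispro keep titrating glargine and "receive another glucose-lowering intervention, if needed per clinical judgment of investigator, and will continue participating in the trial according to the protocol".
- **8.3.6.2**: "Rescue medication will be prescribed as add-on to study intervention(s), and participants will continue to follow the protocol-specified visit schedule".
- **8.3.6.3** (pancreatitis): "the participant must discontinue therapy with investigational product(s), but will continue in the study on another glucose-lowering regimen".
- **8.3.6.7** (hypersensitivity): a participant who stops product permanently may receive another agent "and will continue in the trial to collect all planned efficacy and safety measurements".

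**The concern.** The 7.2 item is triggered by any reason and any effective agent, and it places study exit before the agent starts. It neither excepts nor cross-refers to the therapy allowed elsewhere. A sulfonylurea or SGLT-2 inhibitor given as rescue is plainly another agent effective for type 2 diabetes, so the item covers exactly the participants whom the other sections retain.

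If a site applied it, three things would follow.

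1. **Treatment-regimen estimand.** Protocol 9.4.1 defines this estimand regardless of adherence or rescue, and the full analysis set keeps the post-event data. A participant who leaves before rescue or replacement has no Week 52 HbA1c, so a value that could have been observed must be imputed.
2. **Imputation donors.** SAP 6.12.1.3 imputes from participants in the same arm who stopped study drug and still had a Week 52 HbA1c. Those who stop and need a new agent would leave that pool. If too few donors remain for the model to converge, the SAP switches the primary treatment-regimen analysis to a return-to-baseline method. Rescued participants still on study drug are not donors under the SAP definition, so this effect does not apply to them.
3. **Rescue endpoint.** Initiation of rescue therapy is a safety outcome (Protocol 3, SAP 4.4). With exit first, the new agent would start off study or in the safety follow-up period, and Protocol 4.1.1.3 says that therapy begun for that period is not counted as rescue.

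Data already collected, including any HbA1c from an early termination visit, would remain.

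**Working it through.** **The text, case by case**

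| Participant | Item in 7.2 | Specific section |
|---|---|---|
| Severe, persistent hyperglycemia, needs rescue | Study exit before the agent; study drug also stops | 8.3.6.2: rescue added to study drug, visits continue |
| Stops tirzepatide for GI symptoms, needs another agent | Study exit before the agent | 6.6.3: stays in study, all planned measurements |
| Stops either study drug, needs another agent | Study exit before the agent | 6.5 and 7.1: stays in study |
| Pancreatitis | Study exit before the agent | 8.3.6.3: stops product, stays in study |
| Severe allergic reaction, product stopped permanently, another agent given | Study exit before the agent | 8.3.6.7: stays in study |

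Each row gives opposite instructions for one participant, and the protocol has no rule on which section prevails.

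**Scale**

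Inputs from Protocol 9.2: 197 per tirzepatide dose, 591 pooled tirzepatide, 591 lispro, SD 1.3%, margin 0.3%, true difference 0, one-sided alpha 0.025, two-sample t-test.

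Standard error = 1.3 × √(1/n₁ + 1/n₂). Noncentrality = 0.3 / standard error. Power is the probability that a noncentral t with n₁ + n₂ − 2 degrees of freedom exceeds the 97.5th percentile of the central t (about 1.96).

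The plan's own figures come first:

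- Each dose, 197 v 591: standard error 0.1069, noncentrality 2.805, power 80.0% (plan: 80%).
- Pooled, 591 v 591: standard error 0.0756, noncentrality 3.967, power 97.7% (plan: 97%).

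Both reproduce.

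The documents give no rate of exit under this item. The rates of 1%, 5% and 10% below are assumptions, applied equally to all arms.

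| Assumed exit | Week 52 values lost (of 1182) | Pooled n | Pooled power | Per-dose n | Per-dose power |
|---|---|---|---|---|---|
| 0% | 0 | 591 v 591 | 97.7% | 197 v 591 | 80.0% |
| 1% | 0.01 × 1182 ≈ 12 | 585 v 585 | 97.6% | 195 v 585 | 79.6% |
| 5% | 0.05 × 1182 ≈ 59 | 561 v 561 | 97.1% | 187 v 561 | 77.9% |
| 10% | 0.10 × 1182 ≈ 118 | 532 v 532 | 96.4% | 177 v 532 | 75.7% |

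By arm, 1% is about 2 participants per tirzepatide dose (0.01 × 197) and 6 on lispro (0.01 × 591).

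These are complete-case figures. The planned treatment-regimen analysis is ANCOVA with multiple imputation, so they show scale and do not predict that analysis. They also say nothing about bias from imputing outcomes that could have been measured, which the documents do not allow to be quantified.

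**The case against.** The strongest reply is that the protocol read as a whole already settles the matter. The item sits under a permissive heading. Where study exit is compulsory the protocol says so: both 7.1 and 7.2 name only pregnancy and type 1 diabetes. Table 10 sorts drug classes into allowed and not allowed for rescue and for use after stopping study drug, which would be pointless if any new agent ended participation. The item can therefore be read as meaning prohibited agents only (GLP-1 receptor agonists, DPP-4 inhibitors, pramlintide). On that view a site would have to disregard several explicit instructions before harm arose. The efficacy estimand is also largely untouched, because its data set already excludes data after rescue or after stopping study drug. Finally, 7.1 speaks of permanent discontinuation of study drug as rare, and 7.2 expects discontinuation to be uncommon.

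Much of this stands. The intended rule is almost certainly to keep these participants in follow-up, literal use of the item is less likely for that reason, the 10% scenario is probably high, and the power effect is small.

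It does not remove the conflict. The item carries its own flat statement that exit precedes the new agent. It does not limit itself to prohibited agents. Even read as permissive, it makes the need for an allowed agent a listed ground for leaving the study, where 7.1 and 8.3.6.2 require follow-up to continue. Section 7.2 is also where a site would look for the rule on study exit.

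**Conclusion.** The concern holds. Protocol 7.2, as written, contradicts 6.5, 6.6.3, 7.1, 8.3.6.2, 8.3.6.3 and 8.3.6.7 on whether a participant who starts allowed rescue or replacement therapy stays in the study. The contradiction is certain from the text. Its effect depends on how many sites act on the item, and the documents give no basis for estimating that.

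On the assumed range of 1% to 10%, between 12 and 118 Week 52 values would be lost, and complete-case power would fall by at most 1.3 percentage points pooled (97.7 − 96.4) and 4.3 points per dose (80.0 − 75.7). The case for correction rests on the treatment-regimen estimand, which needs exactly these post-event outcomes, and on the rescue count. It should be fixed, but the design itself is sound.

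**What to change.** Restrict the item by adding an exception for antihyperglycemic therapy allowed under Sections 6.5, 6.6.3, 7.1, 8.3.6.2, 8.3.6.3 and 8.3.6.7. Deleting it would also resolve the conflict, since withdrawal at the investigator's discretion stays in the list, but the exception keeps a provision for agents the protocol does not permit.

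In either case, state in 7.2 that starting allowed therapy is not a reason to end follow-up, and that scheduled visits and the Week 52 HbA1c continue. This governs data collection only. The choice of treatment remains with the investigator.

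The cost is a one-item wording change or a clarification letter to sites. If made as an amendment, it goes through the ethics approval described in Section 10.1.1. It adds no visits, because the other sections already require them.

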7.2.1. Discontinuation of Inadvertently Enrolled Participants

If the sponsor or investigator identify a participant who did not meet enrollment criteria and was inadvertently enrolled, then the participant should be discontinued from study treatment unless there are extenuating circumstances that make it medically necessary for the participant to continue on study treatment. If the investigator and the sponsor CRP agree it is medically appropriate to continue, the investigator must obtain documented approval from the sponsor CRP to allow the inadvertently enrolled participant to continue in the study with or without treatment with investigational product. Safety follow-up is as outlined in Section 1.3., Section 8.2., and Section 8.3. of the protocol.

